**Table 4–2: Calculation rules for duration of adverse events**

Data availability	Calculation rules
Complete start and end date/times	Duration = end datetime – start datetime
Start date or time imputed	Duration <= end datetime – start datetime
End date or time imputed	For ongoing AEs: 

● Duration >= end datetime – start datetime

 For resolved AEs: 

● Duration <= end datetime – start datetime

**Table 4–2: Calculation rules for duration of adverse events**

Data availability	Calculation rules
Start and end date or time imputed	
For ongoing AEs:
 
 
Duration <math>\geq</math> end datetime – start datetime
 
 
For resolved AEs:
 
Duration <math>\leq</math> end datetime – start datetime

#### 4.1.4 Multicenter studies

Up to two study centers/sites in the US will be used in this study. Study participants will be assigned a unique study participant number which will include a center/site identification number, but no analysis by study center/site will be performed.

#### 4.1.5 Center pooling strategy

If more than one center/site in the US is used in this study, all the data will be pooled together in summaries.

### 4.2 Primary endpoints analysis

#### 4.2.1 Pharmacokinetics

##### 4.2.1.1 Definition of endpoints

The primary PK endpoint is the concentration of rozanolixizumab in breast milk over the 7 day Sampling Period.

The secondary PK endpoints that fall under the primary objective of the study are the estimated daily infant dosage and the relative infant dose of rozanolixizumab from breast milk.

#### Estimated daily infant dosage from breastmilk

The estimated daily infant dosage of rozanolixizumab from breast milk will be calculated based on the concentration of rozanolixizumab in mature human breast milk for the PKs.

The amount of rozanolixizumab that the infant may consume following single rozanolixizumab dosing to the mother will be calculated as follows:

$$1. \text{ Estimated daily infant dosage (mg/kg/day)} = \text{M/P ratio} \times C_{\text{av,plasma}} \times 150\text{mL/kg/day}$$

Where M/P ratio is the milk:plasma ratio based on  $\text{AUC}_{(0-7\text{d})}$  and  $C_{\text{av,plasma}}$  is the average maternal plasma concentration calculated as  $\text{AUC}_{(0-7\text{d}),\text{plasma}}/7 \text{ days}$ .

This is based on the standardized mean milk consumption for a fully breastfed 2-month old infant of 150mL/kg/day.

$$2. \text{ Daily infant dosage (mg/day)} = \sum (\text{total drug concentration in each breast milk collection} \times \text{the expressed milk volume (ml) in each collection}) \text{ for each 24hour period of the 7 days postdose.}$$

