##### **9.3.1.1 Calculation of estimated daily infant dosage and relative infant dose from breast milk**

The estimated daily infant dosage will be used to determine the relative infant dose of rozanolixizumab from breastmilk, both of which are secondary endpoints that fall under the primary objective of the study.

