##### **Estimated daily infant dosage from breast milk**

The estimated daily infant dosage of rozanolixizumab from breast milk will be calculated based on the concentration of rozanolixizumab in mature human breast milk for the PKS.

The amount of rozanolixizumab that the infant may consume following single rozanolixizumab dosing to the mother will be calculated as follows:

1. Estimated daily infant dosage (mg/kg/day) =  $M/P \text{ ratio} \times C_{av, \text{plasma}} \times 150 \text{ mL/kg/day}$

Where M/P ratio is the milk:plasma ratio based on  $AUC_{(0-7d)}$  and  $C_{av, \text{plasma}}$  is the average maternal plasma concentration calculated as  $AUC_{(0-7d), \text{plasma}}/7 \text{ days}$ .

This is based on the standardized mean milk consumption for a fully breastfed 2-month old infant of 150 mL/kg/day.

2. Daily infant dosage (mg/day) =  $\text{total drug concentration in each 24-hour breast milk collection period (over 7 days post-dose)} \times \text{the expressed milk volume}$ .

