#### Relative infant dose from breast milk

The relative infant dose of rozanolixizumab from breast milk will be calculated as follows:

$$\text{Estimated daily infant dosage (mg/kg/day)} / \text{maternal rozanolixizumab dosage (mg/kg/day)} \times 100$$

Where

maternal rozanolixizumab dosage (mg/kg/day)=Actual dose administered/(Day 1 weight\*7)

Plasma PK endpoints will be computed using actual blood sampling time points.

The following exploratory PK parameters will be derived for rozanolixizumab in breast milk:

- $C_{max}$ ,  $t_{max}$ ,  $AUC_{(0-7d)}$
- $Ae_{7d}$  (mg)=cumulative total amount excreted in milk to Day 7
- $Fe=Ae_{7d}/\text{administered dose (mg)} \times 100\%$
- Milk:plasma  $AUC_{(0-7d)}$  ratio

The following exploratory PK parameters will be derived for rozanolixizumab in plasma:

- $C_{max}$ ,  $t_{max}$ ,  $AUC_{(0-7d)}$

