## 6.10.2 PK parameters

When reporting individual data in listings the following rules will apply:

- Individual PK parameters should be reported to 3 significant figures.
- If a parameter cannot be calculated, it should be reported as NE (not estimable i.e. if input data is missing which prevents calculation) or NC (not calculable i.e. if the data were available but the calculation was considered unreliable).

When summarizing the data in tables the following rules will apply:

- Descriptive statistics should be reported to 4 significant figures for the mean, SD, geometric mean, CI, and median and to 3 significant figures for the minimum and maximum. Geometric CV will be reported as a percentage to 1 decimal place.
- If at least two thirds of the study participants have a PK parameter reported then descriptive statistics will be calculated, otherwise only minimum and maximum will be reported for this PK parameter and all other descriptive statistics will be reported as NE (i.e. not estimable).
- A minimum of 3 values are required to calculate summary statistics. If only 2 values are available then these should be presented as the minimum and maximum with other descriptive statistics reported as missing (“-“)

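### The estimated infant dosage is computed through plasma AUC, which cancels out, so a participant with a milk AUC but no estimable plasma AUC would lose both secondary PK endpoints for no gain

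*SAP*

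**What the plan says.** SAP 4.2.1.1 opens by saying that the dosage "will be calculated based on the concentration of rozanolixizumab in mature human breast milk for the PKs". Its first formula, identical in protocol 9.3.1.1, nevertheless has two plasma-dependent factors:

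- the M/P ratio: "Where M/P ratio is the milk:plasma ratio based on" AUC(0-7d);
- Cav,plasma, which in the protocol "is the average maternal plasma concentration calculated as" plasma AUC(0-7d) divided by 7 days.

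The third factor is the infant's intake: "This is based on the standardized mean milk consumption for a fully breastfed 2-month old infant of 150mL/kg/day".

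RID is this dosage divided by the maternal dosage, which the SAP sets out as "maternal rozanolixizumab dosage (mg/kg/day)=Actual dose administered/(Day 1 weight" × 7). That denominator contains no plasma term. Protocol 9.3.1.1 describes the dosage and RID as "both of which are secondary endpoints that fall under the primary objective of the study".

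Four other rules bear on the point:

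- The PK Set (SAP 3) admits a participant with a valid measurement in either plasma or milk.
- SAP 6.9 allows no imputation and treats BLQ values after Cmax as missing.
- SAP 6.10.2 reports an uncalculable parameter as NE ("not estimable i.e. if input data is missing which prevents calculation") or NC. It gives full descriptive statistics only if at least two thirds of participants have a value; otherwise only minimum and maximum are shown.
- SAP Table 6-2 defines the milk:plasma AUC ratio with a factor of 100, as a percentage.

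Neither document gives a mg/kg/day formula that uses milk data alone.

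**The concern.** An endpoint described as resting on milk concentration is made to depend on a second matrix that cannot change its value. Plasma brings no information, but it brings an extra condition that must be met before the endpoint exists for a participant.

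The two quantities at stake are the ones a prescriber would read first: infant dosage in mg/kg/day and RID. With 12 to 15 participants, each avoidable loss costs precision, and enough losses would remove the geometric mean and its interval from the table. The percentage form of the ratio in Table 6-2 is a second hazard on the same route, because formula 1 needs the plain ratio.

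**Working it through.** The plan states no figure to reproduce here, so the check is algebra followed by illustrations.

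**1. Cancellation.** Write Am and Ap for milk and plasma AUC(0-7d) in one participant.

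Dosage = (Am/Ap) × (Ap/7) × 150 = (Am/7) × 150.

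This needs both AUCs over the same window and an individual ratio. The documents define both as AUC(0-7d) and compute parameters per participant.

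**2. Numerical check on invented profiles.** Assume Am = 0.3653 µg·day/mL, dose 560 mg and weight 70 kg.

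- Dosage = 0.3653/7 × 150 = 7.83 µg/kg/day = 0.00783 mg/kg/day.
- Maternal dosage = 560/(70 × 7) = 1.143 mg/kg/day.
- RID = 0.00783/1.143 × 100 = 0.685%.

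Formula 1 gave these same values for plasma AUCs of 6.5, 35.2, 263.3 and 265.5 µg·day/mL, a range of about 40-fold.

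**3. When Ap is not estimable.** Both plasma-dependent factors are undefined, so dosage and RID are NE or NC, although (Am/7) × 150 can still be computed. Routes that may lead there are:

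- a missed draw after discharge, which is allowed from Day 3;
- a last sample as early as 120 h, since the window is 144 h ± 24 h while the AUC runs to 144 h;
- BLQ values after Cmax set to missing.

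The SAP has no rule for when AUC(0-7d) counts as estimable.

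**4. Cost of losses (counts assumed).** At equal SD, the half-width of the 95% CI for the log mean is proportional to t(0.975, n−1)/√n.

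| n | factor | relative to n = 12 |
|---|---|---|
| 12 | 0.635 | 1.00 |
| 10 | 0.715 | 1.13 |
| 9 | 0.769 | 1.21 |
| 8 | 0.836 | 1.32 |

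For 12 participants, two thirds is 8, so a fifth loss leaves only minimum and maximum. The same number applies to 13 or 14 participants; with 15 it takes six.

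**5. Range of loss rates (assumed, n = 12, independent losses).**

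| rate of non-estimable plasma AUC | at least one loss | five or more losses |
|---|---|---|
| 5% | 46% | 0.02% |
| 10% | 72% | 0.4% |
| 20% | 93% | 7% |
| 30% | 99% | 28% |

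**6. Percentage ratio.** If the Table 6-2 number goes into formula 1 unconverted, the example becomes 0.783 mg/kg/day and RID 68.5%, both 100 times too high.

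**7. Window average against the peak day.** Take milk concentration proportional to exp(−kt) − exp(−at), where a corresponds to an assumed appearance half-life of 10 h. The highest 24-hour mean divided by the mean over the six days sampled is 1.97, 1.40 and 1.18 for assumed milk half-lives of 24, 72 and 168 h. Varying the appearance half-life from 5 to 20 h moves these to 2.3–1.7, 1.4–1.3 and about 1.2.

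**The case against.** The strongest reply is that the loss may never happen. A reader might infer that any missed draw, early last sample or trailing BLQ value makes the endpoint NE. The documents do not support that:

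- SAP 6.10.2 reserves NE for missing input that prevents calculation.
- The trapezoidal rule bridges a missed interior draw.
- Actual times are used, and off-time plasma samples stay in the parameter calculations (SAP 4.2.1.2).
- SAP 6.9 drops BLQ points without declaring the AUC unusable.

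This part of the reply stands. These events may cause the loss but do not do so by rule, and no rate is given.

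Other parts also stand. Formula 2 (mg/day), Ae, Fe and milk Cmax need no plasma, so infant-exposure information is not wholly lost. The no-imputation and BLQ rules apply to milk as well, so a milk-only formula removes one of two dependencies. Participants withdrawing before Day 7 may be replaced (protocol 7.2), although that does not cover someone who completes the study with an unusable plasma profile.

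On peak exposure, concentrations per interval, milk Cmax and amounts per 24 hours are already reported, so the peak is not hidden. What is missing is a daily figure in mg/kg/day. A reader might also suppose that expressed volumes are unrepresentative because these women plan to wean, but inclusion criteria 6 and 8 require a maintained and sufficient milk supply.

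None of this supplies a reason to keep plasma in the formula.

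**Conclusion.** The point holds as avoidable missingness in two secondary endpoints. It is not a bias: wherever both AUCs exist, the value is the same with or without plasma.

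The cancellation is exact and needs no assumption beyond the plan's own definitions. The size of the harm is unknown, because the documents give no rate of non-estimable plasma AUC. On the assumed counts, 2 or 3 losses of 12 cost about 13% or 21% in interval width. Reduction of the summary to minimum and maximum is unlikely unless the loss rate is high. The 100-fold hazard is conditional too: it arises only if the Table 6-2 percentage is used unconverted.

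Two stronger readings should be avoided:

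- Dividing milk AUC by the number of days sampled is not equivalent to the present formula. The AUC runs to 144 h, which is six days, so every value would rise by 7/6 (about 17%) while the RID denominator stayed at 7.
- Peak-day ratios of 2.3, 1.6 and 1.4 arise only when the 144 h AUC is divided by 7. Against the six-day average they are about 2.0, 1.4 and 1.2.

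**What to change.** In SAP 4.2.1.1, and in protocol 9.3.1.1 at the next amendment:

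- Define estimated daily infant dosage (mg/kg/day) = milk AUC(0-7d)/7 days × 150 mL/kg/day, with unit conversion stated.
- Keep the milk:plasma AUC ratio as an exploratory endpoint only, so that its percentage form in Table 6-2 no longer feeds the dosage.
- Add to SAP 6.9 a rule for when AUC(0-7d) is estimable in each matrix, including how a last sample before 144 h is handled.

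The 144 h AUC against the 7-day divisor is a separate question. Whatever is decided there should be applied consistently to the dosage and to the RID denominator.

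Optionally, for each 24-hour period report [sum(C × V)/sum(V)] × 150 mL/kg/day and its maximum over the days, where C and V are concentration and volume per collection interval. Both are already recorded.

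The cost is a few lines of SAP text and, if the option is taken, one extra set of table rows. No new data are needed, and the redefinition changes no value for participants with both AUCs.

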#### Relative infant dose from breast milk

The relative infant dose of rozanolixizumab from breast milk will be calculated as follows:

$$\text{Estimated daily infant dosage (mg/kg/day)} / \text{maternal rozanolixizumab dosage (mg/kg/day)} \times 100$$

Where

maternal rozanolixizumab dosage (mg/kg/day)=Actual dose administered/(Day 1 weight\*7)

Plasma PK endpoints will be computed using actual blood sampling time points.

The following exploratory PK parameters will be derived for rozanolixizumab in breast milk:

- $C_{max}$ ,  $t_{max}$ ,  $AUC_{(0-7d)}$
- $Ae_{7d}$  (mg)=cumulative total amount excreted in milk to Day 7
- $Fe=Ae_{7d}/\text{administered dose (mg)} \times 100\%$
- Milk:plasma  $AUC_{(0-7d)}$  ratio

The following exploratory PK parameters will be derived for rozanolixizumab in plasma:

- $C_{max}$ ,  $t_{max}$ ,  $AUC_{(0-7d)}$

### Supporting calculations

The time postpartum on Day 1 will be calculated as:

Time postpartum on Day 1 (weeks) = (Date of dosing - Date of delivery of infant(s))[days]/7

The single maternal dosage levels of rozanolixizumab will be based on body weight on Day 1 predose as follows:

420mg for study participants <50kg,

560mg for participants  $\geq 50\text{kg}$  to <100kg, or

840mg for participants  $\geq 100\text{kg}$

Actual dose administered will be calculated as:

Actual dose administered = Dosage level x Percent of planned dose administered

Where

Percent of planned dose administered = total volume delivered / total volume planned

The total volume planned is recorded in the eCRF.

#### 4.2.1.2 Main analytical approach

All PK analyses will be presented on the PKS.

The concentration of rozanolixizumab in breast milk and plasma will be listed and summarized using descriptive statistics by nominal (scheduled) sampling time points for the PKS. Any plasma concentrations with an actual sampling time deviation of greater than 10% from nominal sampling time will be flagged and excluded from the summary statistics, but will be included in the PK parameter calculations.

Individual study participant concentration-time profiles for rozanolixizumab in breast milk and plasma will be displayed together graphically on the linear and semi-logarithmic scale. Spaghetti plots of the individual concentration-time profiles will be displayed graphically (linear and semi-logarithmic scales) separately for milk and plasma. Geometric mean profiles of rozanolixizumab

concentrations in breast milk and plasma over nominal (scheduled) time will be displayed together graphically on the linear and semi-logarithmic scale. The 95% CIs for the geoMean will be displayed on the linear scale plot only and the LLOQ will be included on all semi-logarithmic scale plots. The midpoint of each milk sampling interval will be used in the plots for both the actual and nominal sampling times for the breast milk concentrations.

The estimated daily infant dosage and relative infant dose will be listed and summarized using descriptive statistics. The amount of rozanolixizumab excreted in each collection interval, and the daily infant dosage (or total amount of rozanolixizumab excreted for each 24-hour milk collection period) will be listed and summarized over the 7 days postdose,

The exploratory PK parameters will be listed and summarized separately for milk and plasma using descriptive statistics.

### **4.3 Secondary endpoints analysis**

#### **4.3.1 Treatment-emergent adverse events**

##### **4.3.1.1 Definition of endpoint**

All adverse events (AEs) will be coded using MedDRA® version 27.1 and characterized as pretreatment and treatment emergent according to the intake of treatment. Adverse events with a start date prior to the first and only dose of treatment will be defined as pretreatment AEs. A TEAE is defined as any AE with a start date/time on or after the dosing of study medication until 8 weeks (56 days) inclusive after dosing of study medication.

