### **2.3 Benefit/risk assessment**

The healthy female study participants included in this study will receive no medical benefit from participation. It is not known whether rozanolixizumab is excreted in human milk or absorbed systemically after ingestion. To remove the risk of exposing infants to rozanolixizumab, only lactating women who have voluntarily decided to cease or suspend breast milk feeding and who have established alternative sources of nutrition for their infant(s) will be eligible to participate in the study. Considering the uncertainty of how long rozanolixizumab could be present in the mammary glands (via binding to mammary tissue FcRn), breast milk feeding or resumption of breast milk feeding will not be allowed between the end of the breast milk Sampling Period and the SFU telephone call 8 weeks after dosing (ie, on Day 57). Participants may decide to resume breast milk feeding 8 weeks after administration of rozanolixizumab, with the agreement that any breast milk collected (to maintain milk supply) during that 8-week period will be discarded. A lactation consultant will be available from the Screening Period up until 30 days after the SFU telephone call to support the cessation and potential resumption of breast milk feeding following the SFU.

Based on rozanolixizumab mechanism of action and observations from the current nonclinical and clinical studies with rozanolixizumab and potential risks generally associated with biologic immunomodulators, treatment with rozanolixizumab may be associated with increased risk of serious infections, aseptic meningitis (drug-induced aseptic meningitis [DIAM]), hypersensitivity reactions including injection site reactions, and may temporarily impair vaccination efficacy.

Headache is the most common side effect of rozanolixizumab. Headaches are mostly mild to moderate and managed with over-the-counter medications. Other side effects include diarrhoea,

pyrexia, nausea, upper respiratory tract infections, arthralgia, rash, injection site reactions, vomiting, myalgia, herpes simplex infections, and aseptic meningitis.

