### **8.3.1 Time period and frequency for collecting AE and SAE information**

All AEs and SAEs will be collected from the signing of the ICF and at the time points specified in the schedule of activities (Section 1.3).

In order to ensure complete safety data collection, all AEs occurring during the study (ie, after the signing of the ICF), including any pretreatment and posttreatment periods required by the protocol, must be reported in the CRF even if no study medication was taken but specific study procedures were conducted. This includes all AEs not present prior to the initial visit and all AEs that recurred or worsened after the initial visit.

All SAEs will be recorded and reported to the sponsor or designee within 24 hours, as indicated in Appendix 3 (Section 10.3). The investigator will submit any updated SAE data to the sponsor within 24 hours of it being available.

The investigator is specifically requested to collect and report to UCB (or its representative) any SAEs (even if the investigator is certain that they are in no way associated with the study medication), up to 30 days from the end of the study for each study participant and to also inform participants of the need to inform the investigator of any SAE within this period. Serious AEs that the investigator thinks may be associated with the study medication must be reported to UCB regardless of the time between the event and the end of the study.

The method of recording, evaluating, and assessing causality of AEs and SAEs and the procedures for completing and transmitting SAE reports are provided in Appendix 3 (Section 10.3).

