#### AEs

Adverse events will be captured from the time of consent until the SFU Visit. All AEs will be coded using the Medical Dictionary for Regulatory Activities (MedDRA).

The occurrence and incidence of treatment-emergent adverse events (TEAEs) will be summarized by MedDRA system organ class and preferred term for the SS. A TEAE is defined as any AE with a start date/time on or after the dosing of study medication until 8 weeks after dosing of study medication. The occurrence and incidence of TEAEs will also be summarized by intensity and by relationship to rozanolixizumab. Adverse events leading to discontinuation and SAEs will also be summarized.

Further details on all safety analyses will be given in the SAP.

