### Follow-up of AEs and SAEs

- The investigator is obligated to perform or arrange for the conduct of supplemental measurements and/or evaluations as medically indicated or as requested by UCB to elucidate the nature and/or causality of the AE or SAE as fully as possible. This may include additional laboratory tests or investigations, histopathological examinations, or consultation with other health care professionals.
- An AE should be followed until it has resolved, has a stable sequelae, the investigator determines that it is no longer clinically significant, or the study participant is lost to follow up. This follow-up requirement applies to AEs, SAEs, and AEs of special interest.
- If a study participant dies during participation in the study or during a recognized follow-up period, the investigator will provide UCB with a copy of any post-mortem findings including histopathology.
- New or updated information will be recorded in the originally completed CRF.
- The investigator will submit any updated SAE data to UCB within 24 hours of receipt of the information.

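### Treatment-emergent AEs are defined by start date alone, so an AE open at dosing that worsens afterwards may be missing from the TEAE tables unless the site opens a new record

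*SAP*

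**What the plan says.** SAP 4.3.1.1 sorts AEs by when they began. On one side, "Adverse events with a start date prior to the first and only dose of treatment will be defined as pretreatment AEs". On the other, "A TEAE is defined as any AE with a start date/time on or after the dosing of study medication until 8 weeks (56 days) inclusive". Protocol 9.4.1 uses the same start-date rule: "A TEAE is defined as any AE with a start date/time on or after the dosing of study medication until 8 weeks after dosing". The pretreatment label appears only in the SAP. Neither section mentions an AE that is present before the dose and becomes worse after it.

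The collection rules are wider than the analysis rule. Protocol 8.3.1 collects AEs from signature of the consent form, and screening may last up to 4 weeks before dosing. What must be reported includes "all AEs that recurred or worsened after the initial visit". For an AE that is already recorded, protocol Appendix 3 (10.3, follow-up of AEs and SAEs) says: "New or updated information will be recorded in the originally completed CRF". Protocol 10.1.5.1 leaves detailed entry instructions to the CRF Completion Guidelines, which are a separate document.

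**The concern.** TEAE occurrence is the secondary safety endpoint. The protocol asks sites to capture worsening, but the analysis has no class for an AE that begins in screening and worsens after rozanolixizumab. If the site updates the existing record, the start date stays before the dose, and the SAP then directs the programmer to call the event pretreatment.

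Any loss goes one way: events can drop out of the treatment-emergent counts and none is added. It could also fall on the event of most interest, since protocol 2.3 states "Headache is the most common side effect of rozanolixizumab". Protocol 10.1.7 and SAP 6.12 name TEAEs and treatment-emergent SAEs as the safety results to be published on registries, so an omission would carry through to the public record.

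The rule is also out of step with the rest of the SAP, which leans towards counting. Missing intensity is treated as severe and missing relationship as related (4.3.1.2). A start date with only the day missing, in the month of dosing, is first set to the dosing day (4.1.3). A marked laboratory abnormality is treatment-emergent if the marked level was absent before dosing (4.5.2), so a mild baseline abnormality that worsens to that level is captured. The AE definition has no equivalent.

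**Working it through.** The documents give no figure to reproduce. The check compares the definition with the recording rules, then follows one example through the outputs.

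**Step 1: does any text require a new record when an open AE worsens?**

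- Protocol 8.3.1: worsened AEs must be reported. It does not say whether as a new entry or an update.
- Protocol 8.2.1: worsening of earlier findings is recorded as an AE. The context is physical examination and vital signs.
- Protocol Appendix 3, AE definition: exacerbation of a pre-existing condition, if chronic or intermittent, is itself an AE. It does not address an acute AE already open in the CRF.
- Protocol Appendix 3, follow-up: updates go to the existing CRF. Onset dates and intensity changes are not mentioned.
- Protocol 10.1.5.1: details are left to the CRF Completion Guidelines.

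No passage requires a new record and none forbids one. The outcome depends on how the site enters the data.

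**Step 2: follow one case.** Take a mild headache that starts in screening, is open at dosing and becomes severe afterwards.

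| SAP output | Limited to TEAEs? | Existing record updated | New record dated at worsening |
|---|---|---|---|
| TEAE incidence, overall and by term (4.3.1.2) | Yes | Missing | Counted |
| Severe TEAEs; TEAEs by maximum intensity (4.3.1.2) | Yes | Missing | Counted as severe |
| Overview line, TEAEs of special monitoring (4.3.1.2) | Yes | Missing | Counted |
| Headache focus category (6.8, Table 6–1) | Yes | Missing | Counted |
| AESM summary for the Safety Set (6.7, Appendix 7) | No limit stated | Counted if marked as AESM on the AE form | Counted if so marked |
| Overview SAE line; table of discontinuation due to AEs (4.3.1.2) | No limit stated | Counted if the event qualifies | Counted if it qualifies |
| Listing of all AEs (4.3.1.2) | No | Shown | Shown |

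The third and fifth rows can therefore give different special-monitoring counts for the same woman.

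**Step 3: weight of one woman.** The only input is the planned number providing data, 12 to 15 (protocol 9.8, SAP 5). Assume that the Safety Set has that size.

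- Effect of one uncounted woman = 1/n.
- n = 15: 1/15 = 6.7 percentage points.
- n = 12: 1/12 = 8.3 percentage points.

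Women who withdraw before Day 7 may be replaced (protocol 7.2), so the Safety Set could be larger. If all 20 planned for screening were dosed, 1/20 = 5.0 points.

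The SAP tabulates non-serious TEAEs above a 5% threshold. With 12 to 15 women, one woman exceeds it, so a missed non-serious event could remove a preferred term from that table if nobody else had it. At n = 20, one woman is exactly 5.0% and does not exceed the threshold.

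**The case against.** A reader might infer that every AE that worsens after dosing is classed as pretreatment, drops out of all special-monitoring counts and survives only in listings. The documents do not support that. The AESM summary in SAP Appendix 7 is for the Safety Set, takes AESMs from the AE form and states no treatment-emergent limit. The overview SAE line and the table of discontinuation due to AEs are not labelled treatment-emergent either.

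Nor is the classification itself certain. Protocol 8.2.1, 8.3.1 and the Appendix 3 AE definition allow worsening to be entered as its own AE, which would then have a post-dose start date and already be a TEAE. A recurrent headache could reasonably be treated as an intermittent condition. The follow-up bullet in Appendix 3 is general, and the CRF Completion Guidelines may already contain the missing instruction.

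The stakes are also limited. The study is single-arm and descriptive, participants are healthy, screening is short, and the all-AE listing for a group this small makes each case visible. AESMs are reported to the sponsor within 24 hours.

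All of this stands, and it limits the point to a gap in the definition. It does not close the gap: the SAP states outright that a pre-dose start makes an AE pretreatment, and neither document contains the recording rule that would make this harmless. The secondary safety endpoint should not depend on an unstated data-entry convention.

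**Conclusion.** The point holds in a conditional form. Both documents define a TEAE by start date/time alone. Unless the site opens a new record, post-dose worsening of an AE already open at dosing is missing from the TEAE-based outputs marked as such in the table above, while the AESM summary and the listings can still show it.

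The size cannot be estimated. The documents do not say how many AEs will be open at dosing, and the number that worsen may be zero. The 6.7 to 8.3 points per woman is an illustration. It assumes a Safety Set of 12 to 15 and that the woman has no other post-dose record that would count her on the same line. It is not a forecast of bias. The change is worth making before database lock because it costs little and concerns a named endpoint.

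**What to change.** Choose one of two mechanisms.

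1. **Change the definition.** In SAP 4.3.1.1 and protocol 9.4.1, define a TEAE as an AE that starts on or after dosing, or that starts before dosing and increases in intensity or becomes serious on or after dosing, within the 56-day window. Amend the SAP's pretreatment sentence to match. This needs the date of worsening to be available in the data; the documents do not show whether the AE form holds it.
2. **Keep the start-date rule and fix the recording.** State in the protocol and the CRF Completion Guidelines that each post-dose worsening of an AE open at dosing is entered as a new AE record with its own start date.

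If both are used, link the records. Otherwise the earlier record and the new one could both qualify, and the event would be counted twice in the event totals that SAP 4.3.1.2 requires. It would also help to say whether the Appendix 7 AESM summary covers all AESMs or only treatment-emergent ones, so that it can be reconciled with the overview line.

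The cost is one clause in each document, or one recording instruction, issued through the usual amendment route. No new assessments are needed.
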